10.1.1. Overall Response Rate

Under the IMWG uniform response criteria, a response is defined as being either a stringent complete response (sCR), complete response (CR), very good partial response (VGPR) or a partial response (PR). Investigator's assessment of response will be used for the response analysis. The overall response rate (ORR) is defined as the percentage of subjects with a confirmed disease response (sCR, CR, VGPR, or PR) according to the International Myeloma Working Group International Myeloma Working Group International Myeloma Working Group (IMWG) uniform response criteria, over the number of subjects included in the analysis. For the response to be confirmed, a consecutive disease assessment must achieve the same response or better. Confirmed responses that are documented after the initiation of another anti-myeloma treatment will not be counted as responses. Subjects without a disease assessment will be considered a non-responder for the purpose of the ORR. The ORR shall be presented along with the corresponding Clopper-Pearson 95% confidence interval (CI).

The proportion of subjects in each response category [i.e. sCR, CR, VGPR, PR, stable disease (SD), PD, relapse, relapse from CR, and Not Evaluable] as well as the proportion of subjects without any disease assessment will be calculated.

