10.1.3.2. Progression-Free Survival

Progression Free Survival is calculated as the time from study enrollment, defined as the IVRS enrollment date, until either PD or death (any cause). Subjects without an event (either a documented PD or death) at the time of study end will be censored at the time of their last documented disease assessment or at the IVRS enrollment date if no disease assessment was conducted. A subject with a documented PD directly following a missing assessment, if not having previously had a documented PD, will be censored at the time of the assessment directly preceding the missing assessment.

Missing assessments are defined as 2 or more consecutive missing assessments, considered as > 66 days (during the treatment period) or > 192 days (during the long-term follow-up phase) between the last adequate assessment and the date of the event, or, >94 days if there is no assessment after enrollment and the subject having an event.

Table 1 below includes the event and censoring rules for PFS.

Table 1: Event and Censoring Rules for Progression Free Survival

Scenario	Date Subject has Event or is Censored	Comment
Progression documented at scheduled assessment	EMA and FDA Guidelines: Event date = first disease assessment date where a PD is documented	A subject with a documented PD directly following a missing assessment, if having not

Scenario	Date Subject has Event or is Censored	Comment
		had a PD observed previously, shall be censored at the time of the last documented assessment or the IVRS enrollment date if there is no prior response assessment.
Progression documented between scheduled assessment	EMA Guidelines: Event = date of documented progression. FDA Guidelines: Event data = last scheduled adequate assessment prior to the unscheduled assessment; if no adequate assessment at scheduled visits existed prior to the unscheduled assessment, then event date = date of unscheduled assessment.	
Subject did not progress nor die	EMA and FDA Guidelines: Censored date: date of last adequate assessment without PD; if no adequate assessment existed then censored at date of enrollment.	
Subject died without initial documented progression	EMA and FDA Guidelines: Event date = date of death.	Per FDA Guidelines if the death date is after AMT then the patient is censored at the last assessment date.

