
For events during the treatment period: Death or progression from the follow-up within 2 cycles (2 x 28 +10-day window = 66 days) after the latest of: treatment period discontinuation date, last cycle end date of study drug, and last adequate assessment date during treatment period
 
For events during the long-term follow-up phase: Death or progression within 6 months (6 x 30.25 + 10-day window = 192 days) after the last assessment
	EMA and FDA Guidelines: Event date = date of death or documented progression if occurring before death.	

Scenario	Date Subject has Event or is Censored	Comment

For treatment period: Death or progression from the follow-up more than 2 assessment cycles (2 x 28 +10-day window = 66 days) after the latest of: treatment period discontinuation date, last cycle end date of study drug, and last adequate assessment date during treatment period
 
For long-term follow-up phase: Death or progression from the follow-up more than 2 assessment cycles, i.e. 6 months (6 x 30.25 + 10-day window = 192 days) after the last assessment
	
EMA and FDA Guidelines: Censor date = date of last adequate assessment with evidence of no progression; if no adequate assessment existed then censor at date of enrollment.
	

New anti-myeloma/non-protocol treatment started prior to progression/death
	
EMA Guidelines: Event date = date of documented progression/death.
 
FDA Guidelines: Censor date = date of last adequate assessment with evidence of no progression; if no adequate assessment exists then censor at the date of enrollment.
	

Death or progression during the treatment period after an extended lost-to-follow-up time (two or more missed scheduled assessments)
	
EMA Guidelines: Event date = date of documented progression or death.
 
FDA Guidelines: Censor date = date of last adequate assessment with evidence of no progression; if no adequate assessment exists then censor at the date of enrollment.
	

Abbreviations: CR = complete response; DoR = Duration of response; OS = overall survival; PD = Disease progression; PFS = Progression free survival; PR = Partial response; sCR = stringent complete response; TTP = Time to progression; VGPR = very good partial response.

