- If the month and year of the incomplete stop date are **after** the month and year of the last dose date of the IP, then the first day of the month will be assigned to the missing day.

Missing year

- Not imputed. Included as TEAE.

Impute Missing Disease Diagnosis Dates:

For partial diagnosis dates, January will be assigned to the missing month; and the first day of the month will be assigned to the missing day.

Impute Incomplete Prior Evidence of Disease Progression Dates:

For partial prior disease progression dates, the first day of the month shall be imputed.

Impute Missing Dates in Prior Anti-myeloma Regimen:

For each prior anti-myeloma regimens, the regimen start/stop date, disease progression date, best response date, and date of first response for RR or better, will be collected. If the day of any date is missing, then the first day of the non-missing month will be assigned to the missing day; if month or year of the missing date is missing, then the date will not be imputed and treated as missing.

Impute Missing Dates in Subsequent Anti-myeloma Therapy:

Subjects will be allowed to take other anti-myeloma therapy after discontinuation from the study. The anti-myeloma therapy start/stop date will be collected. If the day of any date is

missing, then the last day of the non-missing month will be assigned to the missing day; if day and month are both missing, the December 31 of the non-missing year will be assigned to the missing day.

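### Partial start dates of subsequent anti-myeloma therapy are imputed to the latest day with no upper bound, so a start can fall after death and FDA-rule PFS can count a death that should be censored

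*SAP*

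**What the plan says.** Appendix A, on subsequent anti-myeloma therapy, notes that "The anti-myeloma therapy start/stop date will be collected" and then gives a single rule for any such date. With the day missing, "then the last day of the non-missing month will be assigned to the missing day". With less information, "if day and month are both missing, the December 31 of the non-missing year will be assigned to the missing day". It does not distinguish a start from a stop, and it names no limit such as death, last contact, data cut-off or the recorded stop date.

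The start date is used in two places:

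- **PFS under the FDA rules (section 10.1.3.2, Table 1).** One row covers the case "New anti-myeloma/non-protocol treatment started prior to progression/death", and its FDA instruction is "Censor date = date of last adequate assessment with evidence of no progression; if no adequate assessment exists then censor at the date of enrollment". The row for death without documented progression adds: "Per FDA Guidelines if the death date is after AMT then the patient is censored at the last assessment date". I read AMT as anti-myeloma treatment.
- **ORR (section 10.1.1).** "Confirmed responses that are documented after the initiation of another anti-myeloma treatment will not be counted as responses".

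The EMA column of Table 1 counts progression or death whether or not new therapy was given, and OS does not use the date. FDA-rule PFS is a planned output (Table 14.2.5.2 and Figure 14.2.3.2).

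**The concern.** For a stop date, the last day of the known period is a common conservative choice. For a start date it is the latest value possible. The FDA rule asks whether new therapy came before the event, and a start placed on the last day of the month or year can never come before an event in that same period. When the event is a death, the result is also impossible: a subject cannot start therapy after dying.

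At stake is whether FDA-rule PFS does what Table 1 intends. A death on the next therapy, with no earlier documented progression, should be censored at the last adequate assessment. Under the imputation rule it is counted as an event. The error runs one way: it can only turn FDA-rule censorings into events.

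Appendix A guards against part of this elsewhere. For adverse events and for prior or concomitant medications, a partial start in a period after the first month or year on study drug goes to the first day of that period, and a start that lands after a known stop date is reset to the stop date. Neither safeguard is repeated for subsequent therapy.

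**Working it through.** The SAP states no figure on this point, so there is none to reproduce. The check applies the rule as written.

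**1. How late the imputed start is.** Assume the true start is uniform over the known period.

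- Day missing, 31-day month: lateness = 31 − d for true day d. Range 0 to 30; mean = (0 + 1 + … + 30)/31 = 465/31 = 15 days.
- Day and month missing, 365-day year: lateness = 365 − d. Range 0 to 364; mean = 364/2 = 182 days.

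**2. Worked dates.**

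- Therapy truly starts on 5 March, is recorded as March, and the subject dies on 20 March without documented progression. Imputed start: 31 March, 31 − 20 = 11 days after death. Death is not after the imputed start, so the FDA censoring does not trigger.
- Therapy is recorded by year only and the subject dies on 10 June. Imputed start: 31 December, 20 + 31 + 31 + 30 + 31 + 30 + 31 = 204 days after death. Same outcome.
- Therapy start is recorded as March with a complete stop date of 25 March. Imputed start: 31 March, 6 days after the stop.

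**3. Where the gap rule already censors.** Table 1 censors, under both guidelines, a death or progression from follow-up that comes too late. The limit is 2 × 28 + 10 = 66 days after the latest of treatment discontinuation, last cycle end and last adequate on-treatment assessment. In long-term follow-up it is 6 × 30.25 + 10 = 191.5, taken as 192 days, after the last assessment. The censoring date is the last adequate assessment, as under the FDA new-therapy rule.

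For the death on 10 June (non-leap year), the imputation error matters only if the reference date is on or after 5 April (66 days earlier) under the treatment-period limit. Under the long-term limit the last assessment must be on or after 30 November of the previous year (192 days earlier). With older reference dates the subject is censored anyway.

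**4. How often an event could fall in the interval.** Assume an exponential time from new therapy to first event, with median M months. Then λ = ln 2/(M × 30.4167), and the share is the mean over all possible true start days of 1 − exp(−λ × lateness).

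| Assumed median M (months) | Day missing | Day and month missing |
|---|---|---|
| 2 | 15.3% | 76.2% |
| 4 | 8.1% | 57.8% |
| 6 | 5.5% | 45.8% |
| 12 | 2.8% | 27.8% |

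These are shares of subjects with a partial start date and no progression before the new therapy, not of all subjects. They count progression as well as death and ignore the gap rule, so for the death case they overstate. The medians are assumptions; the SAP gives none.

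**The case against.** The strongest defence is that a late start protects the usual sequence, in which the subject progresses, stops study drug and then switches. Planned pomalidomide dosing covers 21 of 28 days (section 8.6) and disease assessments fall on Day 1 of the next cycle (section 3.1), so progression is typically documented some days after the last dose. Imputing the earliest possible start could place new therapy before that progression and censor a true event. This objection stands for progression, and a blanket earliest-start rule should not replace the present one. It does not reach death without documented progression, where the order is known: any therapy actually recorded began before death.

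It is also fair that the gap rule removes many late events, most of all for year-only dates. Subsequent regimens are recorded every 84 ± 14 days, which makes year-only starts less likely, although that is an inference. The stakes are limited too. The primary endpoint is adverse-event incidence, no formal hypothesis tests are planned, and FDA-rule PFS is presented beside EMA-rule PFS.

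A reader might infer three stronger things that the SAP does not support:

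- *That responses to the next therapy inflate ORR.* A response must be confirmed at a consecutive assessment, and section 3.1 schedules only one efficacy assessment after study drug stops, so the effect is negligible.
- *That time to subsequent therapy is overstated.* Section 3.3 lists no such endpoint.
- *That the censoring rule fails for every partial date.* It fails only when the event lies between the true and the imputed start.

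**Conclusion.** The rule needs correcting for one defined situation. A subject has a partial start date for subsequent therapy, dies in the same month or year without documented progression, and is not already censored by the 66- or 192-day rule. The SAP then counts an FDA-rule PFS event that Table 1 means to censor. Separately, the rule allows starts after death and after a recorded stop date, which cannot be defended in any listing or derivation.

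The lateness is 0 to 30 days (mean 15) or 0 to 364 days (mean 182), given a uniform true start in a 31-day month or a 365-day year. The effect on the PFS estimate cannot be computed because the number of partial dates is not given; it may be small. EMA-rule PFS, OS and the primary safety endpoint are unaffected. DoR and TTP borrow the PFS rules without saying which guideline column applies, so whether they are touched cannot be settled from the text.

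**What to change.** Amend Appendix A as follows:

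1. Give separate rules for partial start and partial stop dates of subsequent anti-myeloma therapy.
2. Bound an imputed start below by the last study-drug dose and above by the earliest of stop date, last contact, data cut-off and death. State that any recorded subsequent therapy is treated as started before death when the FDA death rule is applied. The cap alone is not enough: a start set equal to the death date would still fail a test that death came after it.
3. Cap imputed stop dates at death, last contact and data cut-off.
4. Where the order of a partial start and a documented progression is truly unknown, keep the stated convention. Report FDA-rule PFS under the earliest and the latest feasible start as a sensitivity analysis.

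The cost is one more derivation, one more sensitivity table and slightly fewer FDA-rule events. No additional data need to be collected.

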Appendix B: Tables Graphs and Listings

Tables Section 14.

Table Number	Table Title
14.1.1	Analysis Populations
14.1.2.1	Subject Disposition – Treatment Phase: All Populations
14.1.2.2	Subject Disposition – Long-term Follow-up Phase: All Populations
14.1.3	Summary of Reasons for Screen Failure: Screen Failure Subjects
14.1.4	Subjects Enrolled by Study Site: Intention to Treat Population
14.1.5	Summary of Protocol Violations: Intention to Treat Population
14.1.6	Summary Demographic and Baseline Characteristics: All Populations
14.1.7	Baseline Disease Characteristics: All Populations
14.1.8	Medical History: All Populations
14.1.9	Prior Cancer History: All Populations
14.1.10	Prior Medications: All Populations
14.1.11	Prior Therapies: All Populations
14.1.12	Summary of Prior Anti-myeloma Therapies by Drug Class: All Populations
14.1.13	Summary of Last Prior Anti-myeloma Therapies by Drug Class: All Populations
14.1.14	Refractory Status to Selected Prior Anti-myeloma Therapies: All Populations
14.1.15	Summary of Prior Anti-myeloma Treatment Lines and Regimens: All Populations
14.1.16	Evidence of Progression Status to Last Anti-myeloma Therapies: All Populations
14.1.17	Prior Cancer Surgeries for this Disease: All Populations
[REDACTED]	[REDACTED]
14.1.19	Prophylactic Medications During the Treatment Period: Safety Population
[REDACTED]	[REDACTED]

14.1.21	Summary of Prior Venous Thromboembolic Events: All Populations
14.1.22	Summary of Cytogenetic Data: All Populations
14.2.1.1	Summary of Overall Response and Response Rates: All Populations
14.2.1.2	Overall Survival Follow-up: All Populations
14.2.2	Summary of Time to Response (TTR): All Populations
14.2.3	Summary of Duration of Response (DoR): All Populations
14.2.4	Summary of Time to Progression (TTP): All Population
14.2.5.1	Summary of Progression Free-Survival (PFS): According to EMA Guidelines: All Populations
14.2.5.2	Summary of Progression Free-Survival (PFS): According to FDA Guidelines: All Populations
14.2.6	Summary of Overall Survival (OS): All Populations
14.2.7	Summary of Subsequent Anti-myeloma Therapy: Intention to Treat Population
14.2.8	Summary of CC-4047 Plasma Concentrations (ng/mL) by Cycle: Pharmacokinetic Population
14.3.1.1	Summary of Treatment Duration: Safety Population
14.3.1.2.1	Summary of Dose Information: Safety Population
14.3.1.2.2	Summary of Dose Information by Cycle: Safety Population
14.3.1.3.1	Summary of Dose Reductions: Safety Population
14.3.1.3.2	Summary of Dose Reductions by Cycle: Safety Population
14.3.1.4.1	Summary of Dose Interruptions: Safety Population
14.3.1.4.2	Summary of Dose Interruptions by Cycle: Safety Population
14.3.2.1	Summary of Treatment Emergent Adverse Events: Safety Population
14.3.2.2.1	Treatment Emergent Adverse Events: Safety Population
14.3.2.2.2	Treatment Emergent Adverse Events with CTCAE Grade 2 or Higher Infections: Safety Population
14.3.2.3	Treatment Emergent Adverse Events with CTCAE Grades 3 or 4: Safety Population
14.3.2.4.1	Treatment Emergent Adverse Events Related to Any Study Drug: Safety Population
14.3.2.4.2	Treatment Emergent Adverse Events Related to Pomalidomide: Safety Population
14.3.2.4.3	Treatment Emergent Adverse Events Related to Low-Dose Dexamethasone: Safety Population
14.3.2.5.1	Treatment Emergent CTCAE Grade 3 or 4 Adverse Events Related to Any Study Drug: Safety Population

14.3.2.5.2	Treatment Emergent CTCAE Grade 3 or 4 Adverse Events Related to Pomalidomide: Safety Population
14.3.2.5.3	Treatment Emergent CTCAE Grade 3 or 4 Adverse Events Related to Low-Dose Dexamethasone: Safety Population
14.3.2.6.1	Cause of Death During Treatment Period: Safety Population
14.3.2.6.2	Cause of Death During First 60 Days of Treatment: Safety Population
14.3.2.6.3	Cause of Death After 28 Days of End of Treatment: Safety Population
14.3.2.6.4	Cause of Death: Safety Population
14.3.2.6.5	Cause of Death During Screening Period: Non-enrolled Subjects
14.3.2.7	Treatment Emergent Grade 5 Adverse Events: Safety Population
14.3.2.8	Treatment Emergent Serious Adverse Events: Safety Population
14.3.2.9.1	Treatment Emergent Serious Adverse Events Related to Any Study Drug: Safety Population
14.3.2.9.2	Treatment Emergent Serious Adverse Events Related to Pomalidomide: Safety Population
14.3.2.9.3	Treatment Emergent Serious Adverse Events Related to Low-Dose Dexamethasone: Safety Population
14.3.2.9.4	Treatment Emergent Serious Adverse Events Leading to Discontinuation of Any Study Drug: Safety Population
14.3.2.9.5	Treatment Emergent Serious Adverse Events Leading to Discontinuation of Pomalidomide: Safety Population
14.3.2.9.6	Treatment Emergent Serious Adverse Events Leading to Discontinuation of Low-Dose Dexamethasone: Safety Population
14.3.2.10.1	Treatment Emergent Adverse Events Leading to Discontinuation of Any Study Drug: Safety Population
14.3.2.10.2	Treatment Emergent Adverse Events Leading to Discontinuation of Pomalidomide: Safety Population
14.3.2.10.3	Treatment Emergent Adverse Events Leading to Discontinuation of Low-Dose Dexamethasone: Safety Population
14.3.2.11.1	Treatment Emergent Adverse Events Leading to Reduction of Any Study Drug: Safety Population

14.3.2.11.2	Treatment Emergent Adverse Events Leading to Reduction of Pomalidomide: Safety Population
14.3.2.11.3	Treatment Emergent Adverse Events Leading to Reduction of Low-Dose Dexamethasone: Safety Population
14.3.2.12.1	Treatment Emergent Adverse Events Leading to Interruption of Any Study Drug: Safety Population
14.3.2.12.2	Treatment Emergent Adverse Events Leading to Interruption of Pomalidomide: Safety Population
14.3.2.12.3	Treatment Emergent Adverse Events Leading to Interruption of Low-Dose Dexamethasone: Safety Population
14.3.2.13.1	Treatment Emergent Adverse Events by CTCAE Grade 1/2 and 3/4: Safety Population
14.3.2.13.2	Treatment Emergent Adverse Events by CTCAE Grade: Safety Population
14.3.2.14.1	Treatment Emergent Grade 3 or 4 Adverse Events Related to Any Study Drug by CTCAE Grade: Safety Population
14.3.2.14.2	Treatment Emergent Grade 3 or 4 Adverse Events Related to Pomalidomide by CTCAE Grade: Safety Population
14.3.2.14.3	Treatment Emergent Grade 3 or 4 Adverse Events Related to Low-Dose Dexamethasone by CTCAE Grade: Safety Population
14.3.2.15.1	Treatment Emergent Adverse Events by Cycle: Safety Population
14.3.2.15.2	Treatment Emergent Grade 3 or 4 Adverse Events by Cycle: Safety Population
14.3.2.16.1	Summary of Treatment Emergent Adverse Events of Interest: Safety Population
14.3.2.16.2	Treatment Emergent Adverse Events of Interest: Safety Population
14.3.2.16.3	Treatment Emergent CTCAE Grade 3 or 4 Adverse Events of Interest: Safety Population
14.3.2.16.4.1	Treatment Emergent Adverse Events of Interest Related to Any Study Drug: Safety Population
14.3.2.16.4.2	Treatment Emergent Adverse Events of Interest Related to Pomalidomide: Safety Population
14.3.2.16.4.3	Treatment Emergent Adverse Events of Interest Related to Low-Dose Dexamethasone: Safety Population
14.3.2.16.5.1	Treatment Emergent CTCAE Grade 3 or 4 Adverse Events of Interest Related to Any Study Drug: Safety Population

14.3.2.16.5.2	Treatment Emergent CTCAE Grade 3 or 4 Adverse Events of Interest Related to Pomalidomide: Safety Population
14.3.2.16.5.3	Treatment Emergent CTCAE Grade 3 or 4 Adverse Events of Interest Related to Low-Dose Dexamethasone: Safety Population
14.3.2.16.6	Treatment Emergent Serious Adverse Events of Interest: Safety Population
14.3.2.16.7.1	Treatment Emergent Serious Adverse Events of Interest Related to Any Study Drug: Safety Population
14.3.2.16.7.2	Treatment Emergent Serious Adverse Events of Interest Related to Pomalidomide: Safety Population
14.3.2.16.7.3	Treatment Emergent Serious Adverse Events of Interest Related to Low-Dose Dexamethasone: Safety Population
14.3.2.16.7.4	Treatment Emergent Serious Adverse Events of Interest Leading to Discontinuation of Any Study Drug: Safety Population
14.3.2.16.7.5	Treatment Emergent Serious Adverse Events of Interest Leading to Discontinuation of Pomalidomide: Safety Population
14.3.2.16.7.6	Treatment Emergent Serious Adverse Events of Interest Leading to Discontinuation of Low-Dose Dexamethasone: Safety Population
14.3.2.16.8.1	Treatment Emergent Adverse Events of Interest Leading to Discontinuation of Any Study Drug: Safety Population
14.3.2.16.8.2	Treatment Emergent Adverse Events of Interest Leading to Discontinuation of Pomalidomide: Safety Population
14.3.2.16.8.3	Treatment Emergent Adverse Events of Interest Leading to Discontinuation of Low-Dose Dexamethasone: Safety Population
14.3.2.16.9	Treatment Emergent Adverse Events of Interest by CTCAE Grade 1/2 and 3/4: Safety Population
14.3.2.16.10	Treatment Emergent Adverse Events of Interest by CTCAE Grade: Safety Population
14.3.2.16.11	Treatment Emergent Neutropenia by GCSF Usage on Study: Safety Population
14.3.2.16.12.1	Treatment Emergent Arterial Thrombotic Events With and Without Prophylaxis Medications: Safety Population

14.3.2.16.12.2	Treatment Emergent Venous Thrombotic Events With and Without Prophylaxis Medications: Safety Population
14.3.2.16.12.3	Treatment Emergent DVT With and Without Concurrent Pulmonary Embolism [a]: Safety Population
14.3.2.16.13.1	Treatment Emergent Neuropathy by Baseline Neuropathy Status: Safety Population
14.3.2.16.13.2	Time to Onset of Neuropathy: Safety Population
14.3.2.16.13.3	Time to Improvement/Resolution of Neuropathy from Baseline: Safety Population (Subjects with Improvement/Resolution of Baseline Neuropathy)
14.3.2.16.13.4	Time to Worsening/New Incidents of Neuropathy from Baseline: Safety Population (Subjects with Worsening Baseline of Neuropathy or New Incidents of Neuropathy)
14.3.2.16.13.5	Neuropathy Still Ongoing at Treatment Discontinuation: Safety Population (Subjects Who had Treatment Emergent Neuropathy with Neuropathy Ongoing at Baseline)
14.3.2.16.14.1	Treatment Emergent Grade 3 or Higher Neutropenia and Concurrent Infections and Infestations Within Two Weeks: Safety Population
14.3.2.16.14.2	Treatment Emergent Grade 3 or Higher Infections and Infestations and Concurrent Neutropenia Within Two Weeks: Safety Population
14.3.2.16.14.3	Treatment Emergent Grade 3 or Higher Thrombocytopenia and Concurrent Hemorrhage and Bleeding Within Two Weeks: Safety Population
14.3.2.16.14.4	Treatment Emergent Grade 3 or Higher Hemorrhage and Bleeding and Concurrent Thrombocytopenia Within Two Weeks: Safety Population
14.3.2.16.14.5	Treatment Emergent Thrombocytopenia and Concurrent Hemorrhage and Bleeding Within Two Weeks: Safety Population
14.3.2.16.14.6	Treatment Emergent Haemorrhage and Bleeding and Concurrent Thrombocytopenia within Two Weeks: Safety Population
14.3.2.16.15.1	Summary of Second Primary Malignancies (SPM): Safety Population
14.3.2.16.15.2	Summary of Second Primary Malignancies: Time to Onset, Dosing Summary and Incidence Rate per 100 Person-years: Safety Population
14.3.2.16.15.3	Summary of Second Primary Malignancies (SPM): Safety Population Subjects Who Died
14.3.2.16.15.4	Summary of Second Primary Malignancies (SPM): Safety Population Subjects Who are Alive

14.3.2.16.15.5	Summary of Hospitalisations by Primary Cause: Safety Population
14.3.2.16.16	Summary of Non-Treatment Emergent Adverse Events: Intention to Treat Population
14.3.2.17	Treatment Emergent Adverse Events of Special Interest: Deep Vein Thrombosis/Pulmonary Embolism or Polyneuropathy: Safety Population
14.3.2.18	Treatment Emergent Adverse Events of Special Interest Meeting CTCAE Grade 3 or 4 Criteria: Deep Vein Thrombosis/Pulmonary Embolism or Polyneuropathy: Safety Population
14.3.4.1.1	Shift of CTCAE Grades from Baseline to Worst During Study in Laboratory Values (Chemistry): Safety Population
14.3.4.1.2	Shift of CTCAE Grades from Baseline to Worst During Study in Laboratory Values (Hematology): Safety Population
14.3.4.2.1	Shift from Baseline to Worst During Study in ECOG Performance Status: Safety Population
14.3.4.2.2	Shift from Baseline to Best During Study in ECOG Performance Status: Safety Population

Figures Section 14.

Figure Number	Figure Title
14.2.1	Kaplan-Meier Curve for Duration of Response: Intention to Treat Population
14.2.2	Kaplan-Meier Curve for Time to Progression: Intention to Treat Population
14.2.3.1	Kaplan-Meier Curve for Progression Free Survival Based on EMA Guidelines: Intention to Treat Population
14.2.3.2	Kaplan-Meier Curve for Progression Free Survival Based on FDA Guidelines: Intention to Treat Population
14.2.4	Kaplan-Meier Curve for Overall Survival: Intention to Treat Population
14.2.5	Waterfall Plot of Maximum Change in M-Protein from Baseline: Intention to Treat Population
14.2.6	Box-Whisker Plot of the Plasma Concentrations by Cycle
14.3.1	Time to Onset of Hematologic and Solid Tumor Second Primary Malignancies: Safety Population

Listings Section 16.

Listing Number	Title of Listing
16.2.1	Discontinued Subjects
16.2.2	Protocol Violations
16.2.3	Participation in Previous Celgene Studies
16.2.4.1	Demographic and Baseline Characteristics
16.2.4.2	Medical History
16.2.4.3	Disease Diagnosis
16.2.4.4	Prior Anti-myeloma Therapy
16.2.4.5	Prior Radiation Therapy for Myeloma
16.2.4.6	Prior Cancer Surgery for Myeloma
16.2.4.7.1	Prior Stem Cell Transplant for Myeloma
16.2.4.7.2	Prior Therapies for Stem Cell Transplant Conditioning
16.2.4.8	Prior Bisphosphonate Therapy for Bone Lesions
16.2.4.9.1	Evidence of Most Recent Disease Progression
16.2.4.9.2	Evidence of Disease Progression with Last Lenalidomide-containing Regimen
16.2.4.9.3	Evidence of Disease Progression with Last Bortezomib-containing Regimen
16.2.4.10	Prior Medications
██████	████████████████████
██████	██
16.2.4.13	Cytogenetic Assessment
16.2.4.14	Skeletal Survey
16.2.4.15	Bone Marrow Assessment
16.2.4.16	Venous Thromboembolic Event
16.2.4.17	Pregnancy Status and Test Results
16.2.4.18	Subject Eligibility
16.2.4.19	Prior Cancer History

16.2.4.20	Prior Cancer History II – Diagnostic Exams for Cancer Within 6 months Prior to Screening
16.2.4.21	Prior Procedures for Cancer Not Under Study
16.2.4.22	Prior Radiation Treatment for Cancers not Under Study
16.2.4.23	Prior Regimen Treatment for Cancers not Under Study
16.2.5	Study Drug Record: Pomalidomide and Low-Dose Dexamethasone
16.2.6.1	Investigator Assessment of Response (IMWG Criteria)
16.2.6.2	Variables for Determination of Myeloma Response
16.2.6.3	Clinical Plasmacytomas Assessment
16.2.6.4	Radiological Plasmacytomas Assessment
16.2.6.5.1	Subsequent Anti-myeloma Therapy
16.2.6.5.2	Subsequent Stem Cell Transplant for Myeloma
16.2.6.5.3	Subsequent Therapies for Stem Cell Transplant Conditioning
16.2.6.6	Follow-up Therapies
16.2.6.7	Long-term Progression Follow-up
16.2.6.8	Survival Follow-up
16.2.6.10	Individual CC-4047 Plasma Concentrations (ng/mL): Pharmacokinetic Population
16.2.7.1.1	Treatment Emergent Adverse Events
16.2.7.1.2	Pre-treatment and Post-treatment Adverse Events
16.2.7.1.3	Treatment Emergent Adverse Events Leading to Pomalidomide Discontinuation
16.2.7.1.4	Treatment Emergent Adverse Events Leading to Low-Dose Dexamethasone Discontinuation
16.2.7.1.5	Treatment Emergent CTCAE Grade 3 or 4 Adverse Events
16.2.7.1.6	Grade 5 Treatment Emergent Adverse Events
16.2.7.1.7	Treatment Emergent CTCAE Grade 2 or Higher Infections and Concomitant Antibiotic Medication
16.2.7.2	Serious Adverse Events
16.2.7.3.1	Deaths During Treatment Period
16.2.7.3.2	Deaths During First 60 Days of Treatment
16.2.7.3.3	Deaths After 28 Days of End of Treatment
16.2.7.3.4	Deaths for Enrolled Subjects
16.2.7.3.5	Deaths During Screening Period: Non-enrolled Subjects

16.2.7.4	Adverse Events of Clinical Interest
16.2.8.1.1	Local Laboratory - Chemistry
16.2.8.1.2	Local Laboratory - Hematology
16.2.8.1.3	Local Laboratory – Urinalysis
16.2.8.1.4	Local Laboratory - Renal Function Assessment
16.2.8.1.5	Local Laboratory – Immunoglobulins
16.2.8.2	Local Serum Free Light Chain Assessment
16.2.8.3	Vital Signs
16.2.8.4	ECG
16.2.8.5	ECOG Performance Status
16.2.8.6	Healthcare Resource Utilisation
16.2.8.7	Second Primary Malignancies
16.2.8.8	Second Primary Malignancies Procedures
16.2.8.9	Second Primary Malignancy Regimen Therapy
16.2.8.10	Second Primary Malignancy Radiation Therapy
